12.3.4 Attribution Definitions

The relationship, or attribution, of an adverse event to the study therapy regimen or study procedure(s) will initially be determined by the site investigator and recorded on the appropriate AE electronic case report form (AE/SAE eCRF). Final determination of attribution for safety reporting will be determined by the IND sponsor (DAIT/NIAID). The relationship of an adverse event to study therapy regimen or procedures will be determined using the descriptors and definitions provided above.

For additional information and a printable version of the NCI-CTCAE manual, consult the NCI-CTCAE web site: <http://ctep.cancer.gov/reporting/ctc.html>.

Table 12.3.4 Attribution of Adverse Events

Code	Descriptor	Relationship (to primary investigational product and/or other concurrent mandated study therapy or study procedure)
UNRELATED CATEGORY		
1	Unrelated	The adverse event is clearly not related: there is insufficient evidence to suggest a causal relationship.
RELATED CATEGORIES		
2	Possible	The adverse event has a reasonable possibility to be related; there is evidence to suggest a causal relationship.
3	Definite	The adverse event is clearly related.

12.4 Collection and Recording of Adverse Events

12.4.1 Collection Period

Adverse events (including SAEs) will be collected from the time of consent, until a subject completes study participation or until 10 days after he/she prematurely withdraws (without withdrawing consent) or is withdrawn from the study.

12.4.2 Collecting Adverse Events

Adverse events (including SAEs) may be discovered through any of these methods:

- Observing the subject.
- Interviewing the subject [e.g., using a checklist, structured questioning, diary, etc.].
- Receiving an unsolicited complaint from the subject.
- In addition, an abnormal value or result from a clinical or laboratory evaluation can also indicate an adverse event, as defined in 12.3.3 Grading and Attribution of All Other Adverse Events

12.4.3 Recording Adverse Events

Throughout the study, the investigator at the site will record adverse events and serious adverse events as described previously (Section 12.2, *Definitions*) on the appropriate AE/SAE eCRF regardless of the relationship to study therapy regimen or study procedure.

Once recorded, an AE/SAE will be followed until it resolves with or without sequelae, or until the end of study participation, or until 10 days after the subject prematurely withdraws (without withdrawing consent)/or is withdrawn from the study, whichever occurs first.

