6.4. Premature Discontinuation of Investigational Product

Participants, who are prematurely discontinued for safety reasons after receiving at least one dose of investigational product during the Challenge Visit, will not be replaced. Participants who are prematurely discontinued, but who did not receive a dose of investigational product may be replaced.

Study procedures may be prematurely discontinued for any participant for any of the following reasons:

1. SAE related to investigational product
2. Anaphylactic reaction grade 2 or 3 (see Table 12.3.1c)
3. Inability to tolerate the dose escalation during the NAC due to excessive discomfort/symptoms
4. Reduction in FEV₁ of more than 15% from baseline and/or reduction of PEF by more than 20% from baseline and inability to perform spirometry due to administration of rescue medications during the course of the nasal allergen challenge.
5. Development of any serious medical illness whose natural history, sequela, or treatment would be worsened or impaired by continuation in the protocol

7. Other Medications

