11.1. Participant Completion

Phase 1 participants are considered to have completed the study once they have completed either the Challenge Visit and 30-day Follow-Up Visit after Phase 1b, Challenge Visit and 6-10-day Follow-up visit for participants who did not consent to the 30-day Follow-up Visit, or the Challenge Visit and Second Follow-Up Phone Visit for participants who did not consent to the 6-10 or 30 day Follow-Up Visits. If participants refuse to participate in Phase 1b, they are considered to have completed the study after they have completed the Challenge Visit and Follow-Up Clinic Visit (or Additional Follow-Up Phone Visit for participants who do not consent to the mechanistic blood draw.) Phase 2 participants are considered to have completed the study once they have completed the Challenge Visit and 30-day Follow-Up Visit. If participants do not agree to the 30-day Follow-Up Visit, they are considered to have completed the study after the Follow-Up Clinic Visit after Phase 2 (or Additional Follow-Up Phone Visit for participants who do not consent to the mechanistic blood draw at 6-10 days.)

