11.2. Participant Stopping Rules and Withdrawal Criteria

Participants may be prematurely terminated from the study for the following reasons:

1. The participant elects to withdraw consent from all future study activities, including follow-up.
2. The participant dies.
3. The Investigator no longer believes participation is in the best interest of the participant.
4. SAE related to investigational product
5. Anaphylactic reaction grade 2 or 3 (see Table 12.3.1c)
6. Inability to tolerate the NAC prior to reaching a sneezing score of 3 or a TNSS ≥ 8 (Phase 1) or a TNSS ≥ 6 (Phase 2) due to excessive discomfort or symptoms
7. Epistaxis occurring during the Challenge visit
8. The need to start immunotherapy or any chronic immunosuppressive medications in the period between the Screening and Challenge Visits
9. Require a dose of greater than 500 mcg of fluticasone per day or the equivalent of another inhaled corticosteroid to maintain asthma control in the period between the Screening and Challenge Visits

10. Inability to restrict use of antihistamines, nasal steroids, nasal decongestants, nasal anticholinergics or cromolyn prior to the NAC according to the period specified in the ICAC medication washout guidelines described in the MOP for Protocol ICAC-27
11. Development of any serious medical illness whose natural history, sequela, or treatment would be worsened or impaired by continuation in the protocol
12. Participant is "lost to follow-up," as defined in the MOP for Protocol ICAC-27.

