11.4. Follow-up after Early Study Withdrawal

Participants who withdraw from the study after receiving one dose of investigational product will be followed as described in Section 6.4 Premature Discontinuation of Investigational Product.

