11.5. Study Stopping Rules

The study may be prematurely terminated for the following reasons:

Study enrollment and treatment will be suspended pending expedited review of all pertinent data after the occurrence of:

1. 1 death regardless of relationship to the investigational product
2. 1 anaphylactic reaction grade 3 or higher possibly related to the investigational product
3. ≥ 1 nonfatal SAE possibly related to the investigational product
4. If considered related to the study procedures or treatments, in at least 2 participants
 - a. Anaphylactic reaction grade 2 or higher.
 - b. Reduction of FEV1 by more than 15% from baseline and/or reduction of PEF by more than 20% from baseline and inability to perform spirometry due to administration of rescue medications in phase 1 or phase 2.

If the study is stopped due to meeting the above criteria, it may not be resumed until all pertinent information is discussed with DAIT NIAID, NIAID Asthma and Allergy DSMB, and the central IRB, and all parties concur with the resumption of the study. Local IRBs will be informed of the study stoppage and the DSMB/central IRB's decision on resumption of the study.

The study may be terminated by DAIT/NIAID or the NIAID Asthma and Allergy DSMB upon review of any observations, events, or new information that merit such action.

12. Safety Monitoring and Reporting

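### Section 12.4.3 ends follow-up of unresolved SAEs at end of participation or 10 days after withdrawal, and Section 11.4 refers follow-up of dosed withdrawals to a section that contains none

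*Protocol*

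**What the plan says.** Protocol Section 12.4.3 gives three end points for a recorded event. The first two are "Once recorded, an AE/SAE will be followed until it resolves with or without sequelae, or until the end of study participation". The third is 10 days after a participant leaves without withdrawing consent, or is withdrawn. The earliest of the three governs, for AEs and SAEs alike. Section 12.4.1 puts the same 10-day limit on collecting new events after withdrawal.

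Under Section 11.4, participants who leave after a dose "will be followed as described in Section 6.4 Premature Discontinuation of Investigational Product". Section 6.4 holds replacement rules (those discontinued "for safety reasons after receiving at least one dose of investigational product during the Challenge Visit, will not be replaced") and a list of five reasons that opens "Study procedures may be prematurely discontinued for any participant for any of the following reasons".

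Section 11.2 begins "Participants may be prematurely terminated from the study for the following reasons". Its list includes a related SAE, grade 2 or 3 anaphylaxis, inability to tolerate the challenge, and epistaxis at the Challenge Visit.

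Section 11.1 defines completion: "Phase 2 participants are considered to have completed the study once they have completed the Challenge Visit and 30-day Follow-Up Visit". A child who does not agree to that visit completes at the 6-10 day clinic visit, or at the phone call that replaces it.

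Under Section 11.5, one nonfatal SAE possibly related to the product suspends the study, and "it may not be resumed until all pertinent information is discussed with DAIT NIAID, NIAID Asthma and Allergy DSMB, and the central IRB". SAP Section 8 adds no follow-up rule.

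**The concern.** Safety is one of the two primary objectives, and the plan reports events by severity, seriousness and relatedness. Under SAP Section 8.2 each event is entered once, at its highest severity, and under SAP Section 8.1 missing safety information is not imputed. If active follow-up stops while an event is still open, the recorded maximum severity may not be final and the outcome may be unknown. This matters most for SAEs and for events that count toward Section 11.5, because the bodies deciding on resumption need to know how those events ended. Nothing in the protocol requires anyone to find out once the cut-off has passed. For pregnancies the protocol takes the opposite course: Section 12.6 follows them to conclusion.

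**Working it through.** The plan states no figure to reproduce. The check is of text and of durations.

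**1. The reference from 11.4 to 6.4.** Section 11.4 promises follow-up and names Section 6.4 as its description. Section 6.4 says who may be replaced and why study procedures may be discontinued. It gives no call, visit, assessment or duration. The reference is empty.

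**2. The cut-off in 12.4.3.** Follow-up ends on the earliest of resolution, end of participation, and withdrawal day + 10. For an event that does not resolve, only the last two remain. Neither depends on seriousness, relatedness or whether the event counts toward Section 11.5.

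**3. Days of follow-up for an open event.** Inputs: 10 days after withdrawal (12.4.1, 12.4.3); day 6-10 contact (8.5, 8.6); 30-day visit with AE assessment, optional in Phase 2 (8.6, 8.9); repeat challenge 30-365 days after the first (8.9). The challenge is day 0, and withdrawal is assumed to fall on day 0.

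| Participant | Follow-up ends | Compared with withdrawal on day 0 |
|---|---|---|
| Withdrawn on challenge day | 0 + 10 = day 10 at latest | reference |
| Phase 2, accepts 30-day visit | day 30 | 30 − 10 = 20 days longer |
| Phase 2, declines 30-day visit | day 6-10 | 0 to 4 days shorter |
| Phase 1b, takes 30-day visit (days from repeat challenge) | day 30 | 20 days longer |
| Adult completing 1a, 1b and the 30-day visit (days from first challenge) | 30 + 30 = 60 to 365 + 30 = 395 | 50 to 385 days longer |

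If withdrawal falls on day d, the limit moves to day d + 10. It reaches day 30 when d = 20, so the 20-day gap is specific to withdrawal on the challenge day.

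**4. An ambiguity in the same sentence.** Because the earliest limit governs, and withdrawal may itself be the end of participation, a literal reading could close follow-up on the withdrawal day. The 10-day limit was presumably meant to prevent that, but the text does not say so.

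**5. Provisions that might close the gap.** Section 12.5.1 has the SAE form updated when further details arrive, but creates no duty to seek them. Section 8.5 gives extra follow-up for significant asthma symptoms at the next-day call, with no stated duration and no cover for other reactions. Section 8.8 permits unscheduled visits but does not require them. None of these requires an open SAE to be followed to resolution.

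**The case against.** The strongest reply is that the plan is less bare than Section 11.4 suggests. Section 8.5 sends the next-day call to each participant and Section 8.6 asks all participants back at day 6-10; neither is conditional on finishing the challenge. That stands, and it makes the Section 11.4 correction largely the repair of a reference. It does not supply a rule for an SAE still open at the cut-off.

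It can also be said that exposure is one session per challenge, that expected symptoms last hours (Section 5.1.1), and that the SAP does not plan to tabulate resolution. Most events will indeed close well within 10 days. The concern is with the few that do not, and for those the severity, which is tabulated, may still change. The sponsor, DSMB and central IRB can withhold agreement to resume while an outcome is unknown, but that does not oblige a site to obtain it.

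Three stronger readings are tempting, and the documents do not support them:

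- A reader might infer that harmed participants are in general followed for less time than unharmed ones. Termination under Section 11.2 is discretionary, and stopping study procedures under Section 6.4 is not leaving the study, so a participant with a reaction may stay on the normal schedule. The contrast holds only against those who accept the 30-day visit or go on to Phase 1b.
- A reader might infer that anyone withdrawn for a reaction gets at most 10 days. The 10 days run from withdrawal, not from the challenge.
- A reader might infer that a death after day 10 escapes reporting and the first stopping rule. That rule has no time limit, and Section 12.2.4 also covers deaths occurring during the study.

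**Conclusion.** The point holds in a limited form. Followed exactly, Section 12.4.3 ends active follow-up of an unresolved SAE or stopping-rule event on a calendar date, and the section named in 11.4 for follow-up of dosed withdrawals describes none. For withdrawal on the challenge day the limit is day 10, against day 30 for a participant who accepts the optional visit. For a Phase 2 child who declines that visit it is day 6-10, whether or not an event is open.

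The number of participants affected cannot be estimated, because the protocol gives no expected rate of SAEs or withdrawals; with 35 participants it is likely to be small. The Manual of Procedures was not available and may say more, but Section 11.4 points to Section 6.4 and not to the Manual. The correction is worth making because it protects the outcome data on the most serious events. It does not affect the design, the sample size or the response analysis.

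**What to change.** 1. In Section 12.4.3, exempt SAEs and any event counting toward Section 11.5 from the end-of-participation and 10-day limits. For participants who have not withdrawn consent, follow these events until resolved or stable and record the outcome on the eCRF. State that for all other events in withdrawn participants the 10-day limit applies, so that withdrawal is not itself read as the end of follow-up.
2. As a secondary correction, point Section 11.4 to the contacts in Sections 8.5 and 8.6 instead of Section 6.4, and word it to cover participants withdrawn by the investigator as well as those who choose to leave, as Section 11.3 already does.

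The cost is a change of protocol wording and a few extra contacts for a small number of participants. No analysis in the SAP needs to change.

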12.5 Reporting of Serious Adverse Events and Adverse Events

12.5.1 Reporting of Serious Adverse Events to the IND Sponsor DAIT/NIAID

This section describes the responsibilities of the site investigator to report serious adverse events to the IND sponsor via the SAE eCRF. Timely reporting of adverse events is required by 21 CFR 312 and ICH E6 guidelines.

Site investigators will report to the SACC (Rho Federal) and DAIT/NIAID Medical Monitor all serious adverse events (see Section 12.2.4, *Serious Adverse Event*), regardless of relationship or expectedness within 24 hours of discovering the event.

For serious adverse events, all requested information on the AE/SAE eCRF will be provided. However, unavailable details of the event will not delay submission of the known information. As additional details become available, the AE/SAE eCRF will be updated and submitted. Every time the SAE eCRF is submitted, it should be signed by the investigator.

For additional information regarding SAE reporting, contact Rho Product Safety:

Rho Product Safety

12.5.2 Reporting to Health Authority

After an adverse event requiring 24 hour reporting (per Section 12.5.1, *Reporting of Serious Adverse Events to the IND Sponsor*) is submitted by the site investigator and assessed by the IND sponsor (DAIT/NIAID). The IND sponsor must report an event to the appropriate health authorities using one of these two options:

12.5.2.1 Standard Reporting (report in the IND Annual Report)

This option applies if the AE is classified as one of the following:

- Serious, expected, suspected adverse reactions (see Section 12.2.2, *Suspected Adverse Reaction*, and Section 12.2.3, *Unexpected Adverse Event*).
- Serious and not a suspected adverse reaction (see Section 12.2.2, *Suspected Adverse Reaction*).
- Pregnancies.

Note that all adverse events (not just those requiring 24-hour reporting) will be reported in the IND Annual Report.

12.5.2.2 Expedited Safety Reporting

This option, with 2 possible categories, applies if the adverse event is classified as one of the following:

Category 1: Serious and unexpected suspected adverse reaction [SUSAR] (see Section 12.2.1.1, *Suspected Adverse Reaction* and Section 12.2, *Unexpected Adverse Event* and 21 CFR 312.32(c)(1)i).

The sponsor must report any suspected adverse reaction that is both serious and unexpected. The sponsor (DAIT/NIAID) must report an adverse event as a suspected adverse reaction only if there is evidence to suggest a causal relationship between the study drug and the adverse event, such as:

1. A single occurrence of an event that is uncommon and known to be strongly associated with drug exposure (e.g., angioedema, hepatic injury, or Stevens-Johnson Syndrome);
2. One or more occurrences of an event that is not commonly associated with drug exposure, but is otherwise uncommon in the population exposed to the drug (e.g., tendon rupture);
3. An aggregate analysis of specific events observed in a clinical trial (such as known consequences of the underlying disease or condition under investigation or other events that commonly occur in the study population independent of drug therapy) that indicates those events occur more frequently in the drug treatment group than in a concurrent or historical control group.

Category 2: Any findings from studies that suggests a significant human risk

The sponsor shall report any findings from other epidemiological studies, analyses of adverse events within the current study or pooled analysis across clinical studies or animal or *in vitro* testing (e.g. mutagenicity, teratogenicity, carcinogenicity) that suggest a significant risk in humans exposed to the drug that would result in a safety-related change in the protocol, informed consent, investigator brochure or package insert or other aspects of the overall conduct of the study.

The sponsor (DAIT/NIAID) must notify the FDA, and all participating investigators of expedited Safety Reports within 15 calendar days; unexpected fatal or immediately life-threatening suspected adverse reaction(s) shall be reported as soon as possible or within 7 calendar days.

Study investigators are responsible for SAE reporting to the respective IRB as mandated by the IRB.

12.5.3 Reporting of Adverse Events to Central IRB

All adverse events, including expedited reports, will be reported in a timely fashion to the central IRB in accordance with applicable regulations and guidelines. All Safety Reports to the FDA shall be distributed by the sponsor (DAIT/NIAID) or designee to all participating investigators for central IRB submission.

12.6 Pregnancy Reporting

The investigator shall be informed immediately of any pregnancy in a study subject. A pregnant subject will not undergo the NAC. If pregnancy occurs after the NAC procedure has occurred, the investigator shall counsel the subject and discuss the risks of continuing with the pregnancy and the possible effects on the fetus. Monitoring of the pregnant subject shall continue until the conclusion of the pregnancy. If pregnancy is detected during the study screen and prior to any study procedures, no pregnancy monitoring will be required.

The investigator shall report to the Statistical and Clinical Coordinating Center (SACCC) and the sponsor (DAIT/NIAID) all pregnancies within 1 business day of becoming aware of the event using the Pregnancy eCRF. All pregnancies identified during the study shall be followed to conclusion and the outcome of each must be reported except as specified above. The Pregnancy eCRF shall be updated and submitted to the SACCC when details about the outcome are available.

Information requested about the fetal outcome shall include:

- Gestational age at delivery
- Birth weight, length, and head circumference
- Gender
- Appearance, pulse, grimace, activity, and respiration (APGAR) score at 1 minute, 5 minutes, and 24 hours after birth, if available
- Any abnormalities.

Should the pregnancy result in a congenital abnormality or birth defect, an SAE must be submitted to the SACCC and the sponsor (DAIT/NIAID) using the SAE reporting procedures described above.

12.7 Reporting of Other Safety Information

An investigator shall promptly notify the SACCC and DAIT/NIAID via email when an “unanticipated problem involving risks to subjects or others” is identified, which is not otherwise reportable as an adverse event.

12.8 Review of Safety Information**12.8.1 Medical Monitor Review**

The DAIT/NIAID Medical Monitor shall receive monthly reports from the SACCC compiling new and accumulating information on AEs, SAEs, and pregnancies recorded by the study site(s) on appropriate eCRFs.

In addition, the DAIT/NIAID Medical Monitor shall review and make decisions on the disposition of the SAE and pregnancy reports received by the SACCC (See Sections 12.5.1, Reporting of Serious Adverse Events to the IND Sponsor DAIT/NIAID and 12.6, Pregnancy Reporting.

12.8.2 DSMB Review

The DAIT NIAID and SACCC will provide the DSMB with listings of all SAEs on an ongoing basis including quarterly reports of all SAEs. Furthermore, the DSMB will be informed of expedited reports of SAEs.

12.8.2.1 Planned DSMB Reviews

The NIAID Asthma and Allergy Data and Safety Monitoring Board (DSMB) shall review safety data at least yearly during planned DSMB Data Review Meetings. Data for the planned safety reviews will include, at a minimum, a listing of all reported AEs and SAEs.

The DSMB will be informed of an Expedited Safety Report in a timely manner. An SAE which the Medical Monitor determines to be an unexpected safety risk will be sent to the DSMB immediately.

12.8.2.2 *Ad hoc* DSMB Reviews

In addition to the pre-scheduled data reviews and planned safety monitoring, the DSMB may be called upon for *ad hoc* reviews. The DSMB will review any event that potentially impacts safety at the request of the protocol chair or DAIT/NIAID. In addition, any occurrence of meeting one of the study stopping rules as described in Section 11.5 will trigger an *ad hoc* comprehensive DSMB Safety Review. After review of the data, the DSMB will make recommendations regarding study conduct and/or continuation.

12.8.2.2.1 Temporary Suspension of enrollment and drug dosing for *ad hoc* DSMB Safety Review

A temporary halt in both enrollment and drug dosing will be implemented if an *ad hoc* DSMB safety review is required.

13. Statistical Considerations and Analytical Plan

